6.4.6 Patients' Global Impression of Change

The PGIC will be performed at the visits noted in [Table 13-1](#) and [Table 13-2](#) to obtain the subjects' rating of overall improvement.

6.4.7 Genetic Confirmation of FSHD1

Genetic testing for FSHD1 is highly sensitive and specific. The finding of a D4Z4 contraction on chromosome 4q35 likely has a sensitivity of 93% and a specificity of 98% for the diagnosis of clinically defined FSHD. Healthy individuals possess at least 11 D4Z4 repeats, yielding a DNA fragment >38 kb on standard genetic testing. Affected individuals possess between 1 and 10 repeats, yielding DNA fragments ranging from 10 to 38 kb in size. Measurement of the size of the residual D4Z4 sequence on 4q35 forms the basis for genetic testing in FSHD ([Tawil et al, 2015](#)). For this study, only subjects with 1 to 9 repeats will be enrolled. The number of repeats will be calculated by a diagnostic laboratory using the size of the D4Z4 bands on Southern blot testing. The site will enter the number of repeats into the IRT system. Subjects with 10 repeats will be excluded from the study because such individuals tend to have slower progression and are more variable due to the presence of genetic modifiers.

Genetic confirmation must be obtained before the subject is randomized and before the baseline muscle biopsy is performed. Genetic confirmation can come from previous testing, if verified with appropriate documentation from an accredited laboratory. If genetic testing is necessary, the 4-week screening window and activities will not start until the results are obtained and verified by the principal investigator.

Due to the stable transmission of repeat sizes within families, subjects with a clinical diagnosis of FSHD who have a first-degree relative with a genetically confirmed diagnosis of FSHD1 may be entered into the study for screening assessments including MRI. During screening, a confirmatory genetic diagnosis will be conducted. If genetic testing during screening is necessary, the 4-week screening window will not start until the results are obtained and verified by the principal investigator.

[figure not shown]
[figure not shown]
Further detailed handling, processing, storage, and shipping procedures for genetic testing samples are described in a laboratory manual.

Fulcrum Therapeutics

Protocol FIS-002-2019, Version 4.0 (COVID-19 Pandemic Emergency Amendment)

Losmapimod

10 April 2020

6.5 Safety Review Committee

As detailed in [Section 11.1.1](#), a safety review committee (SRC) will review safety data from the study.

6.6 Pregnancy

Pregnancy is not regarded as an AE unless there is a suspicion that the study drug may have interfered with the effectiveness of a contraceptive medication. Any pregnancy that occurs during study participation must be reported as an SAE. Study staff should complete the paper Pregnancy Initial Report Form and fax the form to [REDACTED] Pharmacovigilance within 24 hours of awareness or call the [REDACTED] safety hotline to report.

Fulcrum Therapeutics

Losmapimod

Protocol FIS-002-2019, Version 4.0 (COVID-19 Pandemic Emergency Amendment)

10 April 2020

To ensure subject safety, irrespective of the treatment received by the subject, any pregnancy occurring during study drug administration or until follow-up must be reported within 24 hours of the investigator's knowledge of the event to the sponsor.

If a woman becomes pregnant while on study drug, the study drug must be discontinued immediately. The investigator must counsel the subject and discuss the potential risks to the pregnancy and the possible effects on the embryo or fetus. The pregnancy must be followed up to determine the outcome (including spontaneous miscarriage, elective termination, normal birth, or congenital abnormality) and status of mother and child, even if the subject was discontinued from the study. Pregnancy complications and elective terminations for medical reasons must be reported as an AE or SAE. Spontaneous miscarriages must be reported as an SAE.

Any SAE occurring in association with a pregnancy, that is brought to the investigator's attention after the subject has completed the study and considered by the investigator as possibly related to the study drug must be promptly reported to [REDACTED] and Fulcrum Therapeutics.

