6.2 Safety and Tolerability Assessments

6.2.1 Adverse Events

6.2.1.1 Definitions of Adverse Events

The investigator is responsible for reporting all treatment-emergent AEs (TEAEs) that are observed or reported during the study, regardless of their relationship to study drug or their clinical significance.

An AE is defined as any untoward medical occurrence in a subject enrolled into this study, regardless of its causal relationship to study drug. Subjects will be instructed to contact the investigator at any time after randomization if any symptoms develop.

A TEAE is defined as any event that was not present before exposure to study drug or any event that was already present but worsens in either intensity or frequency after exposure to study drug.

Fulcrum Therapeutics

Losmapimod

Protocol FIS-002-2019, Version 4.0 (COVID-19 Pandemic Emergency Amendment)

10 April 2020

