6.2.1.2 Serious Adverse Events

An SAE is defined as any event that

- results in death
- is immediately life-threatening
- requires inpatient hospitalization or prolongation of existing hospitalization
- results in persistent or significant disability/incapacity
- is a congenital anomaly/birth defect

Important medical events that may not result in death, be life threatening, or require hospitalization may be considered SAEs when, based upon appropriate medical judgment, they may jeopardize the subject or may require medical or surgical intervention to prevent one of the outcomes listed in this definition. Examples of such medical events include allergic bronchospasm requiring intensive treatment in an emergency room or at home, blood dyscrasias or convulsions that do not result in inpatient hospitalization, or the development of drug dependency or drug abuse.

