6.2.1.5 Reporting Adverse Events

All AEs reported or observed during the study will be recorded on the AE page in the eCRF. Information to be collected includes the following:

- drug treatment
- dose
- event term
- time of onset
- investigator-specified assessment of severity and relationship to study drug
- time of resolution of the event
- seriousness
- any required treatment or evaluations
- outcome

Adverse events resulting from concurrent illnesses, reactions to concurrent illnesses, reactions to concurrent medications, or progression of disease states (if unexpected worsening beyond normal disease progression based on investigator's assessment) must also be reported. All AEs must continue to be followed to satisfactory resolution as described in [Section 6.2.1.10](#). The Medical Dictionary for Regulatory Activities (MedDRA) will be used to code all AEs.

Any medical condition that is present at the time that the subject is screened but does not deteriorate should not be reported as an AE. However, if it deteriorates at any time during the study, it should be recorded as an AE.

Please refer to the ReDUX4 Emergency Guidance Document (31 March 2020) for reporting of AEs related to the COVID-19 pandemic.

Reporting for AESIs is described in [Section 6.2.1.3](#).

Fulcrum Therapeutics

Losmapimod

Protocol FIS-002-2019, Version 4.0 (COVID-19 Pandemic Emergency Amendment)

10 April 2020

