9.1. Adverse Events

A treatment-emergent AE (TEAE) is defined as an AE that meets any of the following conditions:

- begins on or after the first dose of study drug and before the stop of study drug + 7 days;
- begins before the first dose of study drug and worsens in severity on or after the first dose of study drug and before the stop of study drug + 7 days;
- is completely missing an onset date and end date;

- is completely missing an onset date and the end date is on or after the first dose of study drug.

For the purpose of inclusion in TEAE tables, incomplete AE onset and end dates will be imputed as follows:

Missing onset dates (where UK and UKN indicate unknown or missing day and month respectively):

- UK-MMM-YYYY: If the AE month and year are different from the month and year of the first dose of study drug, assume 01-MMM-YYYY. If the month and year are the same as the first dose of study drug month and year and the AE end date (after any imputation) is on or after the first dose of study drug, then assume the date of the first dose of study drug. If the AE month and year are the same as the first dose of study drug month and year and the AE end date (after any imputation) is prior to the first dose of study drug, then assume the end date for the onset date.
- DD-UKN-YYYY/UK-UKN-YYYY: If the AE year is different from the year of first dose of study drug, assume DD-JAN-YYYY/01-JAN-YYYY of the collected year. If the AE year is the same as the first dose of study drug year and the AE end date (after any imputation) is on or after the first dose of study drug, then assume the date of the first dose of study drug. If the year is the same as the first dose of study drug and the AE end date (after any imputation) is prior to the first dose of study drug, then assume the end date for the onset date.

Missing end dates (where UK and UKN indicate unknown or missing day and month respectively):

- UK-MMM-YYYY: Assume the last day of the month;
- DD-UKN-YYYY: Assume DD-DEC-YYYY;
- UK-UKN-YYYY: Assume 31-DEC-YYYY.

All AEs will be classified by SOC and PT according to the MedDRA version 22.0 or higher.

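### Protocol 6.6 says pregnancy is not an AE, with one exception, yet requires every pregnancy to be reported as an SAE: a minor safety-reporting error that changes no hypothesis test

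*Protocol*

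**What the plan says.** Protocol 6.6 begins: "Pregnancy is not regarded as an AE unless there is a suspicion that the study drug may have interfered" with a contraceptive medication. The next sentence is "Any pregnancy that occurs during study participation must be reported as an SAE", with no qualifier. The procedure follows: "Study staff should complete the paper Pregnancy Initial Report Form" and fax it to Pharmacovigilance within 24 hours, or telephone the safety hotline. Further on, the section repeats a 24-hour limit for telling the sponsor, requires follow-up to outcome, and asks for complications and medically indicated terminations to be reported as an AE or SAE. It adds: "Spontaneous miscarriages must be reported as an SAE".

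The definitions are elsewhere. Protocol 6.2.1.1: "An AE is defined as any untoward medical occurrence in a subject enrolled into this study". Protocol 6.2.1.2 lists five seriousness criteria: death, immediate threat to life, hospital admission ("requires inpatient hospitalization or prolongation of existing hospitalization"), disability, and congenital anomaly. It adds a medical-judgment clause for other important events. Protocol 6.2.1.6 applies SAE reporting to AEs that meet those criteria, by electronic data capture first. Protocol 6.2.1.5: "All AEs reported or observed during the study will be recorded on the AE page in the eCRF". SAP 9.1: "A treatment-emergent AE (TEAE) is defined as an AE that meets any of the following conditions". SAP 9.1.4 restates the seriousness criteria and has no rule specific to pregnancy.

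**The concern.** Two adjacent sentences give a site opposite instructions for the same foreseeable event. Under the first, an ordinary pregnancy is not an AE. Under the second, it is reported in a category that presupposes an AE and also requires seriousness. Sites could resolve this differently.

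Seriousness of AEs is part of the secondary safety endpoint (Protocol 7.1.2), and serious treatment-emergent AEs are tabulated by arm in SAP Table 14.3.2.1. A pregnancy entered literally as an SAE could therefore appear there although it meets no seriousness criterion. Prompt pregnancy reporting is not in question: the embryo-fetal findings described in Protocol 1.5 justify it.

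**Working it through.** The plan gives no figure to reproduce. The check is a comparison of texts, followed by the weight of one subject.

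**Step 1: does an uncomplicated pregnancy qualify as an SAE?**

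| Test | Source | Uncomplicated pregnancy |
|---|---|---|
| Is it an AE? | Protocol 6.6, first sentence | No, outside the contraceptive-interference exception |
| Must an SAE first be an AE? | Protocol 6.2.1.6 | Yes |
| Does it meet one of the five listed criteria? | Protocol 6.2.1.2, SAP 9.1.4 | No. A later admission or anomaly would be judged on its own |
| Does the important-event clause make it serious? | Protocol 6.2.1.2, SAP 9.1.4 | Only by case-by-case judgment, never for all pregnancies |
| Does 6.6 require it to be reported as an SAE? | Protocol 6.6, second sentence | Yes, always |

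The last row conflicts with the rows above it. Within the exception, pregnancy becomes an AE, but it still has to meet 6.2.1.2 to be serious. The unqualified sentence therefore does not fit the definitions in either branch.

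**Step 2: would it be counted?** SAP 9.1 admits only AEs to the treatment-emergent set, and SAP 9.1.4 admits only events that meet a seriousness criterion. Applied in that order, the definitions exclude the event. Protocol 6.6 also sends pregnancy to its own paper form, whereas AEs go on the eCRF AE page, and Protocol 4.2.1 lists pregnancy under other reasons for withdrawal. The expected count is 0.

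The exception is a site that enters the pregnancy on the AE page and marks it serious because 6.6 says so. An onset between first dose and 7 days after the last falls in the SAP 9.1 window. The SAP does not name pregnancy as something to filter out, so removal would depend on applying the definitions during data cleaning (Protocol 8.1).

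**Step 3: weight of one such entry.** Inputs: 80 enrolled (Protocol 3.1.1), 1:1 allocation (Protocol 5.1), and the Safety Analysis Set as denominator (SAP 4.9.3). Actual arm sizes are not stated, so these are assumptions, with all subjects dosed.

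- Arm of 38: 1/38 = 2.63 percentage points
- Arm of 40: 1/40 = 2.50 percentage points
- Arm of 42: 1/42 = 2.38 percentage points
- Both arms pooled: 1/80 = 1.25 percentage points

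The documents do not give the number of women of child-bearing potential, so no probability of such an event can be derived.

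**The case against.** The strongest defence is that the first sentence governs classification and the second governs reporting, so that reporting as an SAE means reporting with SAE urgency. There is some support for this. The pregnancy route (paper form, fax within 24 hours, hotline) resembles the back-up SAE route in Protocol 6.2.1.6. The separate rules for complications, terminations and miscarriage would be largely redundant if every pregnancy were already an SAE.

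This probably describes the intent, but the text does not say it. The 24-hour limit is stated in its own right, twice. The ordinary SAE route is electronic first, with paper only as a fallback. The same phrase is applied to miscarriage, where actual classification is the natural meaning, although that last point is inference. The redundancy argument also works the other way: it shows that the unqualified sentence does not fit its own section.

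Two parts of the defence do stand. A reader might infer that once a pregnancy has been entered, nothing in the SAP would take it out. That goes too far: SAP 9.1 and 9.1.4 exclude a non-AE, non-serious event by definition, and Protocol 8.1 provides for data cleaning. What is absent is an explicit pregnancy rule. A reader might also take 2.5 points as the expected distortion. It is only the weight of any one subject in an assumed arm of 40. It would arise only if a pregnancy occurred despite required contraception, was uncomplicated, was entered as serious and survived cleaning. The table is by preferred term, so such an entry would also be visible.

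The version 3.0 change log, which concerns pregnancy reporting, describes superseded text and carries no weight here.

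**Conclusion.** The point holds as a minor error in a safety-reporting rule. The unqualified sentence in Protocol 6.6 conflicts with the sentence before it and with the definitions in 6.2.1.2 and 6.2.1.6. A site following it literally would misclassify an uncomplicated pregnancy.

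The effect on the tables is zero when the definitions are applied in order, which is the better reading. Otherwise it is at most one additional subject per such event in a descriptive count: about 2.5 percentage points of an arm, or 2.4 to 2.6 for the assumed arm sizes of 42 down to 38.

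A reader might see this as a flaw in the choice of analysis. The documents do not support that: no estimand, model, analysis set or test depends on it, and the key-endpoint hierarchy in SAP 8.1 is untouched.

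**What to change.** In Protocol 6.6, replace the second sentence with:

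> Any pregnancy during study participation must be reported within 24 hours on the Pregnancy Initial Report Form (or by the safety hotline); it is recorded as an AE or SAE only if the exception above applies or the event meets Section 6.2.1.2.

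Keep the existing rules on follow-up, complications, medically indicated terminations and miscarriage. A line in SAP 9.1.4 stating that uncomplicated pregnancies are not counted as serious treatment-emergent AEs would help but is optional. A separate pregnancy listing is not required; SAP 15.9 plans none, and adding one would be a new output.

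The cost is one sentence, with no new data, staff or procedures and no loss of expedited reporting. Because Protocol 11.2.1 sends amendments to each site's IRB or IEC, the change is best carried in the next amendment and does not justify one of its own.

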6.7 Sample Collections

Processing, storage, and shipping procedures for all clinical laboratory, PK, and target engagement samples are provided in a laboratory manual.

Fulcrum Therapeutics Losmapimod
Protocol FIS-002-2019, Version 4.0 (COVID-19 Pandemic Emergency Amendment) 10 April 2020

7 Statistical and Analytical Plan

Details regarding the statistical methods and definitions will be provided in statistical analysis plan(s) (SAP[s]). Separate SAPs will be prepared for each treatment period of the study. The SAP for the placebo-controlled treatment period will be finalized prior to database lock/freeze for the IA.

Any deviations from the SAP(s) are to be justified in the clinical study reports. Statistical analyses will be performed using Version 9.3 or higher of SAS (SAS Institute, Cary, NC).

Analyses will be generated separately for the placebo-controlled treatment period and the OLE.

7.1 Placebo-Controlled Treatment Period

7.1.1 Primary Endpoint

The primary endpoint of the placebo-controlled treatment period is the change from baseline in DUX4 activity in affected skeletal muscle at Week 16 or Week 36, as measured by QRT-PCR in a panel of DUX4-regulated gene transcripts.

7.1.2 Secondary Endpoints

The secondary endpoints of the placebo-controlled treatment period are as follows:

- Safety and tolerability of losmapimod as defined by the following:
 - Type, frequency, severity, seriousness, and relationship of AEs to losmapimod
 - Incidence of AESIs
 - Number of subjects who prematurely discontinue study drug due to an AE
 - Frequency of clinically significant changes in laboratory test, ECG, vital sign, and physical examination results
- Change from baseline in MFF, LMV, and MFI at Week 12, Week 24 (if applicable) and Week 48

Fulcrum Therapeutics Losmapimod
 Protocol FIS-002-2019, Version 4.0 (COVID-19 Pandemic Emergency Amendment) 10 April 2020

- Plasma concentrations of losmapimod at Week 4, Week 12, Week 16, Week 24, Week 36, and Week 48
- Concentrations of losmapimod in skeletal muscle biopsy at steady state at Week 16 or Week 36
- Target engagement parameters in blood, and skeletal muscle biopsy at Week 16 or Week 36

7.1.3 Exploratory Endpoints

The exploratory endpoints of the placebo-controlled treatment period are as follows:

- Change from baseline in COAs, including
 - RWS with and without weights at Week 4, Week 12, Week 24, and Week 36
 - Classic and FSHD TUG at Week 4, Week 12, Week 24, and Week 36
 - Muscle strength by hand-held quantitative dynamometry at Week 4, Week 12, Week 24, Week 36, and Week 48
 - MFM Domain 1 at Week 12, Week 24, Week 36, and Week 48
 - FSHD-HI at Week 4, Week 12, Week 24, Week 36, and Week 48
 - PGIC at Week 4, Week 12, Week 16, Week 24, Week 36, and Week 48

Change from baseline in inflammatory, immune, apoptotic, and other muscle disease transcripts may be conducted in muscle biopsy at Week 16 or Week 36 and in circulating proteins in plasma and serum at Week 4, Week 12, Week 16, Week 24, Week 36, and Week 48.

7.2 Open-Label Extension

7.2.1 Primary Endpoint

The primary endpoint of the OLE is to evaluate the safety and of losmapimod as defined by the following:

- Type, frequency, severity, seriousness, and relationship of AEs to losmapimod

Fulcrum Therapeutics

Losmapimod

Protocol FIS-002-2019, Version 4.0 (COVID-19 Pandemic Emergency Amendment)

10 April 2020

- Incidence of AESIs
- Number of subjects who prematurely discontinue study drug due to an AE
- Frequency of clinically significant changes in laboratory test, ECG, vital sign, and physical examination results

7.2.2 Secondary Endpoints

- Change from baseline in MFF, LMV, and MFI after long-term dosing (at every-24-week time points)
- Plasma concentrations of losmapimod after long-term dosing (at every-12-week time points)

7.2.3 Exploratory Endpoints

The exploratory endpoints of the OLE are as follows:

- Change from baseline in COAs after long-term dosing (at every-12-week time points), including
 - RWS with and without weights
 - Classic and FSHD TUG
 - Muscle strength by hand-held quantitative dynamometry
 - MFM Domain 1
 - FSHD-HI
 - PGIC
- Change from baseline in inflammatory, immune, apoptotic, and other muscle disease transcripts in circulating proteins in plasma and serum after long-term dosing (at every-24-week time points)

7.3 Sample Size Calculations

Assuming an effect size of 0.70, a sample size of 68 subjects (34 subjects per group) will be needed to provide 80% power with a 2-sided test at a 0.05 significance level to detect a difference between losmapimod and placebo in change from baseline in DUX4 activity in affected skeletal muscle after 16 or 36 weeks (depending upon when the muscle biopsy was

Fulcrum Therapeutics Losmapimod
 Protocol FIS-002-2019, Version 4.0 (COVID-19 Pandemic Emergency Amendment) 10 April 2020
 performed) during the placebo-controlled treatment period. Assuming that approximately 10% of subjects will be non-evaluable, approximately 76 subjects will be randomly assigned at a 1:1 ratio to losmapimod and placebo (38 subjects per group).

7.4 Analysis Sets

The following analysis sets will be used in the statistical analyses.

Full analysis set (FAS): The FAS will consist of all subjects who are randomly assigned to receive double-blind study drug in the placebo-controlled treatment period. All analyses using the FAS will group subjects according to randomized treatment. The FAS is the main analysis population for key study endpoints ([Section 7.6.1](#)). For the secondary and exploratory endpoints, subjects who already transitioned into the OLE portion under protocol version 3.0 will be analyzed as randomized, in this analysis population.

Per-protocol set (PPS): The PPS will consist of all FAS subjects who fulfill all inclusion/exclusion criteria and do not have any significant protocol deviations. All analyses using the PPS will group subjects according to randomized treatment. PPS analyses will be conducted for key study endpoints ([Section 7.6.1](#)) to assess robustness of key study inferences.

Safety analysis set: The safety analysis set will consist of all subjects who receive any study drug. All analyses using the safety analysis set will group subjects according to treatment actually received.

Pharmacokinetic analysis set: The PK analysis set will consist of all subjects who receive at least 1 dose of losmapimod and have evaluable PK data for losmapimod.

Pharmacodynamic analysis set: The PD analysis set will consist of all subjects who receive at least 1 dose of losmapimod and have evaluable PD data for losmapimod.

Open-label losmapimod (Pre-COVID-19) analysis set: This analysis set will consist of subjects who were already transitioned into open-label losmapimod under version 3.0 of the protocol. This analysis set will be used for sensitivity analysis, to assess secondary/exploratory endpoints in this subset of subjects.

Fulcrum Therapeutics

Losmapimod

Protocol FIS-002-2019, Version 4.0 (COVID-19 Pandemic Emergency Amendment)

10 April 2020

Open-label analysis set: The open-label analysis set will consist of all subjects who complete 24 weeks of treatment in the placebo-controlled treatment period and receive at least 1 dose of open-label losmapimod in the OLE. Safety and efficacy analyses in the OLE will be based on this analysis set.

